**Description of Study****Intervention:****SCUT II**

Participants with bacterial corneal ulcers will be randomized in a 1:1:1 fashion to one of three arms:

- Group 1, Standard therapy: topical 0.5% moxifloxacin plus topical placebo plus sham UVX
- Group 2, Early steroids: topical 0.5% moxifloxacin plus topical difluprednate 0.05% plus sham UVX
- Group 3, UVX plus early steroids: topical 0.5% moxifloxacin plus topical difluprednate 0.05% plus UVX

Participants in Groups 1, 2, & 3 will begin study drug (topical difluprednate 0.05% or placebo) within 24 hours after enrollment. Participants in Group 3 will receive UVX (modified Dresden protocol), and Groups 1 & 2 will receive sham UVX. All participants will receive a 30-minute loading dose of topical 0.1% riboflavin and 20% dextran T500 drops every 2 minutes. For Group 3, this will be followed by exposure to UV-A light at a wavelength of 365 nm with an irradiance of 3 mW/cm^2 for 30 minutes for a total dose of 5.4 J/cm^2 (UV lamp: PESCHKE Meditrade GmbH, Hueneberg, Switzerland for India; Avedro KXL System, Waltham, MA, USA for USA). During irradiation patients will continue to receive topical riboflavin at 5-minute intervals. For Groups 1 & 2, sham UVX simulates this experience however the light will be shined adjacent to the patient, careful to avoid exposure to the cornea. In place of riboflavin we will use either saline drops or saline drops dyed with fluorescein. All study participants will have repeat corneal cultures 30 minutes after the UVX or sham UVX procedure.

After UVX/sham UVX and a repeat culture, antibiotics will be initiated. All participants will receive 0.5% topical moxifloxacin drops every 1 hour for 2 days, and then every 2 hours while awake until resolution of the epithelial defect.

Participants in Groups 2 & 3 will receive one drop of 0.05% difluprednate four times daily beginning 24 hours after the initiation of antibiotics for 1 week, decreased by 1 drop weekly for a total of 4 weeks of steroid therapy. Participants in Group 1 will receive topical placebo in place of steroids, with the same medication schedule described above.

**REAGIR**

Participants with fungal, acanthamoeba, or smear/culture negative corneal ulcers will be randomized in a 1:1 fashion to one of two arms:

- Group 4, Sham RB-PDT: topical biguanide (acanthamoeba), moxifloxacin 0.5% (smear/culture negative) or polyene (fungal keratitis) plus sham RB-PDT
- Group 5, RB-PDT: topical biguanide (acanthamoeba), moxifloxacin 0.5% (smear/culture negative) or polyene (fungal keratitis) plus RG-PDT

Participants in Groups 4 and 5 will begin topical antimicrobial at enrollment. We will use every hour topical biguanide for acanthamoeba, moxifloxacin 0.5% for smear/culture negative, and polyene for fungal keratitis. Topical agents will be applied to the affected eye every hour while awake for the first week, then every 2 hours while awake until 3 weeks after enrollment. Thereafter, application will be tapered at the discretion of the treating physician based on response to therapy.

RB-PDT/sham RB-PDT will occur within 48 hours of randomization. For patients with acanthamoeba keratitis, de-epithelialize central 9mm of the cornea. For Group 5, Rose Bengal (0.1% RB in 0.9% sodium chloride) will be applied in 3-minute intervals to the de-epithelialized cornea for 30 minutes followed by irradiation with a 6mW/cm^2 custom-made green LED source for 15 minutes (5.4J/cm^2). They will undergo repeat cornea cultures within 24 hours after the procedure. Participants in Group 4 will undergo a sham procedure using topical balanced salt solution and pen light covered with a green filter.

## REAGIR II

With SCUT II closed to enrollment, participants with typical bacterial corneal ulcers will be randomized to one of two possible treatment arms:

- Group 6, RB-PDT Plus Early Steroids: topical 0.5% moxifloxacin plus topical difluprednate 0.05%/prednisolone acetate 1% plus RB-PDT
- Group 7, Sham RB-PDT Plus Early Steroids: topical 0.5% moxifloxacin plus topical difluprednate 0.05%/prednisolone acetate 1% plus sham RB-PDT

Participants in Groups 6 & 7 will begin topical difluprednate 0.05% (India) or prednisolone acetate 1% (Brazil) within 24 hours after enrollment. The affected eye will receive one drop of 0.05% difluprednate/prednisolone acetate 1% four times daily beginning 24 hours after the initiation of antibiotics for 1 week, decreased by 1 drop weekly for a total of 4 weeks of steroid therapy.

RB-PDT/sham RB-PDT will occur within 48 hours of randomization. For Group 6, Rose Bengal (0.1% RB in 0.9% sodium chloride) will be applied in 3-minute intervals to the de-epithelialized cornea for 30 minutes followed by irradiation with a 6mW/cm^2 custom-made green LED source for 15 minutes (5.4J/cm^2). They will undergo repeat cornea cultures within 24

hours after the procedure. Participants in Group 7 will undergo a sham procedure using topical balanced salt solution and pen light covered with a green filter.

[figure not shown]

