#### **REAGIR II: Corneal Cross-Linking with Rose Bengal**

Participants in Groups 6 and 7 will begin topical difluprednate 0.05% within 24 hours after enrollment.

RB-PDT/sham RB-PDT will occur within 48 hours of randomization. For Group 6, Rose Bengal (0.1% RB in 0.9% sodium chloride) will be applied in 3-minute intervals to the de-epithelialized cornea for 30 minutes followed by irradiation with a 6mW/cm^2 custom-made green LED source for 15 minutes (5.4J/cm^2). Participants in Group 7 will undergo a sham procedure using topical balanced salt solution and pen light covered with a green filter. Participants in both groups will undergo repeat cornea cultures within 24 hours after the procedure.

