#### *Moxifloxacin 0.5%*

Topical moxifloxacin 0.5% is a fluoroquinolone antibiotic that is used to treat bacterial infections. This is standard therapy for bacterial keratitis. Immediately after UVX/sham UVX and repeat culture, all participants will receive topical moxifloxacin drops every 1 hour for 2 days, and then every 2 hours while awake until resolution of the epithelial defect.

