#### *Difluprednate 0.05%/Prednisolone acetate 1%*

Difluprednate 0.05% and Prednisolone acetate 1% are both corticosteroids used to reduce inflammation in the eye. Participants in Groups 2 & 3 will receive one drop of 0.05% difluprednate (India) or prednisolone acetate 1% (Brazil) four times daily beginning 24 hours after the initiation of antibiotics for 1 week, decreased by 1 drop weekly for a total of 4 weeks of steroid therapy.

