**REAGIR II: Dosing schedule for medications**

	Group 6: RB-PDT + Early Steroids		Group 7: Sham RB-PDT + Early Steroids	
	Dose	Duration	Dose	Duration
Moxifloxacin 0.5%	Q 1 hours x 2 days, then Q 2 hours while awake	Until resolution of epithelial defect	Q 1 hours x 2 days, then Q 2 hours while awake	Until resolution of epithelial defect
Steroid (Difluprednate 0.05% or Prednisolone Acetate 1%)	QID	Starting at 24 hours after initiation of antibiotics for 1 week, then decreasing by 1 drop weekly for a total of 4 weeks of steroid therapy	QID	Starting at 24 hours after initiation of antibiotics for 1 week, then decreasing by 1 drop weekly for a total of 4 weeks of steroid therapy
Rose Bengal 0.1% RB in 0.9% sodium chloride	Q2 min	60 minutes		
Homatropine	TID	3 days	TID	3 days

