### 6.3 MEASURES TO MINIMIZE BIAS: RANDOMIZATION AND BLINDING

The DCC at UCSF will create the REDCap database to house the randomization list and store data. Once a patient has been identified for inclusion in the study, the study coordinator will review the inclusion/exclusion criteria checklist, and then input the study eye into the REDCap database.

Patients with bacterial ulcers are eligible for randomization to Groups 1, 2, and 3, while patients with fungal, acanthamoeba, and smear/culture negative ulcers are eligible for randomization to Group 4 or 5. Each study eye will be randomly assigned to a treatment group by REDCap. Randomization will be stratified by site. Stratified, block randomization will ensure that an approximately equal number of patients are randomized to each treatment group by site. In SCUT II (groups 1, 2, 3) exact block size will be randomly permuted (block size of 3 with probability 0.7 and 6 with probability 0.3) and will only be known to the biostatistician. In REAGIR (Groups 4, 5) exact block size will be randomly permuted (block size of 4 with probability 0.7 and 6 with probability 0.3) and will only be known to the biostatistician. Block randomization will be performed using a computer program (Statistical package R; R Foundation for Statistical Computing, Vienna, Austria) by the coordinating site.

Once an eye is enrolled (and only one eye can be enrolled) in the study, the study coordinator will assign the study participant's eye an ID (alpha-numeric code) and organize the procedure in the operating room within 48 hours of enrollment. Once the study participant has been assigned a study participant ID and randomized to treatment group, they will be included in the intent to treat analysis.

The patient, physician performing repeat scraping and clinical follow up, microbiologist and refractionist performing the BSCVA will be masked to treatment arm. Due to the nature of the surgical intervention, the surgeon and technician performing cross-linking will not be masked. All study medications and placebo will be labeled identically to ensure adequate masking of study physicians and patients.

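### The REAGIR II dosing table gives rose bengal the SCUT II riboflavin schedule (every 2 min, 60 min) instead of the RB-PDT schedule, and related dosing and culture text needs the same clean-up

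*Protocol*

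**What the plan says.** **Rose bengal in REAGIR II.** Protocol 6.1.1 says that for Group 6 the dye "will be applied in 3-minute intervals to the de-epithelialized cornea for 30 minutes", followed by 15 minutes of green light at 6 mW/cm². Section 1.1 says the same. The REAGIR II table in 6.1.2 gives a 2-minute interval and a 60-minute duration. The REAGIR table, for the same procedure, gives 3 minutes and 45 minutes. The SCUT II table gives riboflavin 2 minutes and 60 minutes.

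**Steroid and antibiotic start in REAGIR II.** Section 1.1 says "Participants in Groups 6 & 7 will begin topical difluprednate 0.05% (India) or prednisolone acetate 1% (Brazil) within 24 hours after enrollment", and the next sentence has the steroid given "four times daily beginning 24 hours after the initiation of antibiotics for 1 week". Section 6.1.1 repeats the enrollment clock without the Brazilian drug: "Participants in Groups 6 and 7 will begin topical difluprednate 0.05% within 24 hours after enrollment". The steroid paragraph of 6.1.1 and the dosing table use the antibiotic clock ("Starting at 24 hours after initiation of antibiotics for 1 week"). That steroid paragraph, although it sits under REAGIR II, says "Participants in Groups 2 & 3 will receive one drop of 0.05% difluprednate (India) or prednisolone acetate 1% (Brazil) four times daily". The only moxifloxacin start under REAGIR II is "Immediately after UVX/sham UVX and repeat culture, all participants will receive topical moxifloxacin drops every 1 hour for 2 days", word for word the SCUT II sentence.

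**Repeat culture for Groups 6 and 7.** The footnote to the Schedule of Activities (1.3) puts it at the time of cross-linking. Sections 1.1 and 6.1.1 allow up to 24 hours afterwards.

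**REAGIR.** Section 1.1 has hourly antimicrobial drops while awake for one week. The drug paragraphs in 6.1.1 and the table in 6.1.2 have an hourly phase of 2 days. Section 6.1.1 starts the antimicrobial at enrollment, but SAP 6.2 describes the Day 2 culture as taken before antibiotics begin. SAP 6.2 also labels both groups Arm 1 in the Fisher's exact comparison.

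**The concern.** The rose bengal row is an operative dosing figure for the intervention under test, and it disagrees with the procedure text. A site working from the table would apply dye more often than intended. Because the row concerns Group 6 only, the departure would fall on one arm of a feasibility study with 30 participants per arm.

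The other items make the delivered treatment or the meaning of an outcome uncertain. In REAGIR II, the interval between first antibiotic and first steroid cannot be fixed from the text, because the antibiotic start is missing in usable form. The order matters clinically: the reassurance in Protocol 2.3.1 that steroids did not potentiate infection comes from SCUT, where (Protocol 2.2) steroid followed 48 hours of moxifloxacin. In REAGIR, adherence to the hourly phase cannot be judged against two regimens, and a reader of the microbiological result would take an on-treatment culture for an untreated one.

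**Working it through.** **1. Does the rose bengal row reproduce?** Inputs: loading 30 min at 3-min intervals and irradiation 15 min at 6 mW/cm² (Protocol 1.1, 6.1.1); for riboflavin, loading 30 min at 2-min intervals, then 30 min of UV-A with drops every 5 min.

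- Control on the light dose: 6 mW/cm² × 900 s = 5.4 J/cm², the stated figure, so 15 min is internally consistent.
- RB-PDT length: 30 + 15 = 45 min. This matches the REAGIR table, provided its 45 minutes counts irradiation.
- UVX length: 30 + 30 = 60 min. This matches the SCUT II riboflavin row.
- REAGIR II row: 60 min, against 45 min by the text, an excess of 15 min. Loading alone (30 min) does not give 60 either. Both interval and duration equal the riboflavin entry.
- Loading applications: 30/3 = 10 by the text; 30/2 = 15 at the table's interval; ratio 1.5.

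**2. Steroid start in REAGIR II.** Take randomization as the time of enrollment (assumption). Steroid hour = antibiotic hour + 24.

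| Antibiotic start assumed | Antibiotic hour | Steroid hour | Beyond the 24 h limit |
|---|---|---|---|
| At enrollment | 0 | 24 | 0 h |
| After RB-PDT, culture at the procedure (1.3 footnote), latest | 48 | 72 | 48 h |
| After RB-PDT, culture at the end of its 24 h window (1.1, 6.1.1), latest | 48 + 24 = 72 | 96 | 72 h |

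The 48 h comes from 6.3 ("organize the procedure in the operating room within 48 hours of enrollment"); 1.1 and 6.1.1 count the same 48 h from randomization. The last two rows require the moxifloxacin sentence to be read as referring to RB-PDT, which it does not name.

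**3. REAGIR hourly phase, first week.** With w waking hours a day: one-week regimen 7w drops. The 2-day regimen gives 48 + 2.5w if the hourly phase runs round the clock, or 4.5w if only while awake. The documents do not give w; 16 is assumed, with range 14 to 18.

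| w | One week hourly | 2 days, round the clock | 2 days, awake | Ratios |
|---|---|---|---|---|
| 14 | 98 | 83 | 63 | 1.18, 1.56 |
| 16 | 112 | 88 | 72 | 1.27, 1.56 |
| 18 | 126 | 93 | 81 | 1.35, 1.56 |

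**4. REAGIR Day 2 culture.** The antimicrobial starts at hour 0, the procedure takes place by hour 48, and the culture follows within 24 h. The culture can therefore come after up to 48 + 24 = 72 h of treatment. The SAP phrase matches Protocol 9.4.2, which describes SCUT II Groups 1 to 3, where antibiotics follow the procedure and culture.

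**The case against.** **The two steroid sentences can both be met.** This stands. With moxifloxacin at enrollment and steroid at hour 24, the gap is zero. A reader might infer that the two clocks are irreconcilable, but that needs the moxifloxacin sentence to be operative, and its trigger, UVX or sham UVX, does not occur in REAGIR II. The supportable point is narrower: no usable antibiotic start is written for Groups 6 and 7, and the steroid timing depends on it.

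**The REAGIR table is not a clean control.** Partly right. Read literally it gives 45/3 = 15 applications, not 10, and it agrees with the text only if its duration includes irradiation. That reading is well supported, since the riboflavin row also equals loading plus light, but the table should say so.

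**The Manual of Operations may settle all this.** It may; it is not among the documents. Protocol 10.1.10 counts noncompliance with the protocol itself as a deviation, so the protocol text has to be consistent whatever the manual says. The physician's freedom to change therapy (6.5, 6.5.1) does not define the default regimen.

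**The choice of regimen is clinical.** This stands. The documents do not settle when moxifloxacin should begin in REAGIR II. Nor do they settle whether the REAGIR hourly phase should be 2 days or one week; the synopsis text is the more detailed of the two.

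**Conclusion.** The REAGIR II rose bengal row is wrong as written: 60 min against 45, and a 2-min against a 3-min interval, or 1.5 times the intended loading applications. It should be corrected. The related items are genuine inconsistencies in current text: the missing moxifloxacin start and unreconciled culture timing, the wrong group numbers and omitted drug, the two REAGIR hourly regimens, and the SAP culture wording. The 72 to 96 h steroid figure is conditional on applying the UVX sentence to RB-PDT; the drop counts are conditional on the assumed waking hours.

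Three stronger readings are not supported:

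- **A tripled dye dose.** The literal 60/2 = 30 applications against 10 ignores that these tables appear to list total procedure time. By its own text, riboflavin is given 30/2 + 30/5 = 21 times, not 30.
- **A protocol-sanctioned steroid dose before any antibiotic.** Following the enrollment clock together with the UVX sentence could produce that order, but it would breach the 24-hours-after-antibiotic rule in 1.1, 6.1.1 and 6.1.2. It would be a deviation.
- **Bias in the between-arm comparison.** Apart from the rose bengal row, the items apply equally to both arms of each trial. No effect on sample size, alpha, power or the primary analysis follows from any of them.

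**What to change.** 1. **REAGIR II dosing table (6.1.2):** change the rose bengal row to every 3 minutes for 30 minutes of loading, 45 minutes including irradiation. In the REAGIR table, state that 45 minutes includes irradiation.
2. **REAGIR II timing (1.1, 6.1.1):** keep one steroid rule, 24 hours after the first antibiotic dose, and delete the enrollment-based rule. Replace the UVX-based moxifloxacin sentence with a start stated by the investigators. Enrollment is the start that satisfies both current rules, but it would make the Group 6 and 7 repeat culture on-treatment. Protocol 9.4.1 refers to a REAGIR II SAP that is not among the documents, so the investigators should check the effect there. Reconcile the culture timing in the 1.3 footnote with 1.1 and 6.1.1.
3. **REAGIR II steroid text (6.1.1):** change Groups 2 and 3 to Groups 6 and 7, and add prednisolone acetate 1% for Brazil to the opening paragraph.
4. **REAGIR hourly phase:** the investigators confirm one regimen and use it in 1.1, 6.1.1 and 6.1.2. The 2-day regimen is the one in 6.1.1 and the dosing table.
5. **SAP 6.2:** delete the statement that the Day 2 culture precedes antibiotics, describe it as on-treatment, and label RB-PDT as Arm 2.

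Cost: a protocol wording amendment, which needs IRB approval before use (Statement of Compliance), a SAP text edit and a memo to sites. No new data are needed.

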**Study Duration:**

5 years

**Participant Duration:**

12 months

## 1.2 SCHEMA

## 1.3 SCHEDULE OF ACTIVITIES (SOA)

	Visit 1 Day 0	Visit 2 Day 1	Visit 3 Day 2	Visit 4 Day 3	Visit 5 3-Week Follow- Up	Visit 6 3-Month Follow- Up	Visit 7 6-Month Follow- Up	Visit 8 12- Month Follow- Up
Forms								
Consent & Authorization		X						
Baseline Form		X						
Clinical Drawing	X	X			X	X	X	X
VFQ		X					X	
Follow-up Form		X			X	X	X	X
Final Form								X
Procedures								
CXL/Sham CXL			X					
Tests								
IOP	X	X			X	X	X	X
Pain Scale	X	X		X				
AS-OCT	X				X	X	X	X
Confocal Microscopy	X				X	X	X	X
Pentacam Topography	X				X	X	X	X
Clinical Photography*	X				X	X	X	X
Slit Lamp Examination	X	X			X	X	X	X
BSCVA/ETDRS/MRx		X			X	X	X	X
Pinhole Visual Acuity	X							
Culture/Smear	X		X +					
Total Visit Time	2 hours	2 hours	3 hours	0.5	1 hour	1 hour	1 hour	1 hour
*Clinical photographs also taken upon adverse events								
*Repeat scraping and culture of corneal ulcer done at time of CXL for Participants in Groups 1, 2, 3, 6, and 7; and within 24 hours of CXL for Groups 4 and 5								

## 2 INTRODUCTION

## 2.1 STUDY RATIONALE

**Although antibiotics are successful at achieving microbiological cure in infectious keratitis, outcomes are often poor due to corneal scarring.** Randomized trials comparing different antibiotic treatments have not been able to demonstrate superiority of one antibiotic over another. During acute infection pathogens, keratocytes and other inflammatory cells secrete enzymes that promote protein degradation and keratolysis with resultant opacity and irregular astigmatism. Corneal perforation can also result, requiring urgent surgical intervention with therapeutic penetrating keratoplasty (TPK), which has a poor prognosis compared with penetrating keratoplasty (PKP) performed for visual rehabilitation. *Ideal treatment of corneal ulcers would address both the infection and inflammation.*

**The Steroids for Corneal Ulcer Trial (SCUT U10EY015114) Investigated adjuvant topical steroids in addition to antibiotics to reduce the inflammatory response in bacterial ulcers.** The trial failed to find benefit or harm overall; however, pre-specified subgroup analyses suggested that earlier steroid treatment of large, central, non-*Nocardia* ulcers led to better clinical outcomes. These subgroup analyses have led some to conclude that topical corticosteroids *may be beneficial for specific subgroups of culture positive bacterial ulcers, and that they were most effective when administered early with appropriate antibiotics.*

**Corneal cross-linking (CXL) is a novel prospective therapy that may simultaneously reduce both inflammatory cells and bacterial pathogens.** UV-A + riboflavin is effective *in vitro* against common bacterial ocular pathogens, such as *Pseudomonas aeruginosa* and *Streptococcus pneumoniae*. Multiple case reports have suggested potential benefits of UVX for treatment of bacterial keratitis, including resolution of resistant infection, halting of progressive melting and symptomatic improvement. In one small case series bacterial infections resolved even though patients were treated exclusively with photo-chemically activated riboflavin. Therapies to reduce inflammation may improve outcomes, however there are concerns about potentiating infection and poor healing. The possibility that UVX may immediately reduce the burden of infectious organisms makes subsequent anti-inflammatory treatment safer.

**Recently another CXL method has been proposed that uses rose bengal (RB) as the photosensitizer and green light (532 nm) and is termed RB-PDT.** RB-PDT appears to have similar effects on corneal biomechanical properties, is safe for limbal stem cells and endothelium, and demonstrates less toxicity to keratocytes *in vitro* than UVX. *In vitro* studies have demonstrated limited benefit of UVX for fungal or acanthamoeba keratitis, and one randomized clinical trial also did not show a benefit of adjuvant UVX in filamentous fungal keratitis patients. *In vitro* RB-PDT appears to be much more effective against fungal and acanthamoeba isolates. CXL for infectious keratitis is identified in the literature as Rose Bengal Photodynamic Therapy (RB-PDT) and Photoactivated Chromophore for Infectious Keratitis (PACK-CXL).

**Cross-linking may reduce the risk of progressive corneal melting and perforation that can complicate the management of corneal ulcers.** Corneal melting occurs in response to proteolytic enzymes released both from pathogens and leukocytes sent to combat infection. Corneal perforation is a devastating complication, often treated with surgical interventions such as therapeutic penetrating keratoplasty (TPK) which have a poor prognosis compared with penetrating keratoplasty (PKP) performed for visual rehabilitation. UVX corneas show increased *in vitro* resistance to keratolysis by collagenase A. One non-randomized prospective series of 40 patients found a decreased rate of perforation among those treated with UVX compared with controls despite the fact they had on average larger baseline ulcer size. A recent meta-analysis concluded that the probability that UVX was beneficial in inhibiting melting in patients with infectious keratitis was 85% (95% CI 0.77 to 0.91). One *ex vivo* study demonstrated that RB-PDT treated corneas have similarly increased resistance to enzymatic degradation by collagenase A compared to UVX despite less penetration of RB into the corneal stroma.

**Clinical hypotheses are sometimes best addressed through international research collaborations.** While corneal ulceration is an important cause of disability in technologically advanced countries, it occurs 10-fold more frequently in developing countries. Approximately 2 million people form a corneal ulcer every year in India alone. The high burden of disease in South Asia permits investigation of the optimal treatment of infectious keratitis to avoid corneal opacification, a leading cause of blindness worldwide. *Here, we propose an international, 3-arm randomized controlled*

*clinical trial to investigate corneal crosslinking and early topical steroids as adjuvant therapies in the treatment of bacterial corneal ulcers.*

